2.3.3. Per Protocol Analysis Set

The per protocol analysis set (PP) will consist of all participants who received study intervention and who complied with the protocol to allow assessment of the treatment effects. Specifically, this includes randomized participants who comply with the study intervention, have at least the key (ePRO) measurement of KCCQ completed, and do not experience major protocol deviations that may have an impact on estimating the treatment effect. The effectiveness analysis for the primary and secondary endpoints will be repeated for the PP analysis set.

2.3.4. Safety Analysis Set

The safety analysis set includes all randomized participants who received at least 1 dose of study intervention. Summary of available safety data from all sources (claims and patient reported) will be based on this analysis set.

2.4. Definition of Subgroups

Analysis for the primary effectiveness endpoint will be performed for the subgroups identified below.

Subgroup	Definition
Region**	US - East, West, North and South
Age Group	
 • 18-25 • 26-50 • 51-64 • >65
Gender	
 • Male • Female
Race	
 • White • Non-White
Diabetes type	
 • T2DM • No-T2DM
HF – Ejection Fraction type	
 • pEF (preserved ejection fraction) • rEF (reduced ejection fraction)

**Information on region will be based on details available through IHNs.

Additional subgroups may be identified (including those based on combinations of T2DM and HF ejection fraction types) before finalizing the database.

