optional participant satisfaction survey at end of study (via smartphone), step count and floors climbed (via the Fitbit device), medical and pharmacy claims data (including up to 36 months history for eligibility confirmation), HRU and health economics (including hospitalization/readmission due to HF or other reason, ED visits, the duration of stay at each hospitalization/readmission), review of claims for prohibited medications and new diagnoses that may require discontinuation, and adverse events. In addition, information related to outpatient IV diuretics, inotropes and vasodilators and in-patient IV therapies as well will be considered relevant. Note that claims data that involves up to 36 months history to confirm eligibility into this study will not be part of the study database for analysis.

Participants will be of any gender, 18 years of age or older, and will have clinically stable, symptomatic HF with or without type 2 diabetes mellitus (T2DM) with a KCCQ overall summary score <80 prior to randomization, which represents New York Heart Association (NYHA) II and III participants.

Figure 1: Schematic Overview of the Study

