4.1. Demographics and Baseline Characteristics

Table 2 presents a list of the demographic variables that will be summarized by each intervention group, and both combined for the full analysis set (FAS). Demographics will also be summarized by various IHNs (or regions) using the FAS as well as the all randomized analysis set.

Table 2: Demographic Variables

Continuous Variables:	Summary Type	
Age (years)	Descriptive statistics (N, mean, standard deviation [SD], median and range [minimum and maximum], and IQ range). Frequency distribution with the number and percentage of participants in each category.	
Categorical Variables		
Age (18-25 years, 26-50 years, 51-64 years, and ≥65 years)		
Sex (male, female)		
Race ^a (American Indian or Alaska Native, Asian, Black or African American, Native Hawaiian, or, other Pacific Islander, White, Other)		
Diabetes status at baseline (T2DM or no T2DM)		
HF ejection fraction type (HF _r EF or HF _p EF)		

^a If multiple race categories are indicated the Race is recorded as 'Multiple'.

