The main MMRM analyses will be repeated with each subgroup tested separately. Intervention group differences of LS means as well as corresponding 95% CIs within each subgroup level will be presented.

The intervention-by-subgroup interaction p-value will be estimated using a separate MMRM model including intervention, baseline KCCQ value, stratification factor (HFrEF/HFpEF), subgroup, and intervention-by-subgroup interaction term(s). Interactions with p-value < 0.1 will be investigated further to determine the nature of interaction (quantitative or qualitative) and the

association with other subgroups. For qualitative interactions, Gail and Simon (1985) approach¹⁵ may be considered.

Results will be presented in a summary table and in a forest plot. The forest plot will display the “overall” treatment effect, based on the main MMRM analysis, as a reference line. LS means of the intervention group differences, the corresponding 95% CIs, and the numbers of participants in the subgroup levels will be presented in the forest plot.

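### SAP 2.4 puts participants aged exactly 65 in no age subgroup, while Table 2 of the same SAP includes them; sparse age levels also have no merging rule

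*SAP*

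**What the plan says.** The protocol (Section 9.4.2.1 and the synopsis) leaves subgroup definitions to the SAP, so SAP 2.4 is the operative text. It introduces its table with "Analysis for the primary effectiveness endpoint will be performed for the subgroups identified below", and the age row reads "18-25 • 26-50 • 51-64 • >65".

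SAP 4.1, Table 2, bands age for the demographic summary as "Age (18-25 years, 26-50 years, 51-64 years, and ≥65 years". The first three bands are identical and only the last differs. Eligibility has no upper age limit (SAP 1.2: "Participants will be of any gender, 18 years of age or older").

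SAP 5.2.3 says how the levels are used: "The main MMRM analyses will be repeated with each subgroup tested separately", with treatment differences and "corresponding 95% CIs within each subgroup level will be presented", and the number of participants in each level shown on the forest plot. For heterogeneity, "The intervention-by-subgroup interaction p-value will be estimated using a separate MMRM model including intervention", with subgroup and intervention-by-subgroup terms, and interactions with p below 0.1 are looked at further.

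The main model uses an unstructured covariance over Weeks 2, 4, 6 and 12. If it does not converge, simpler structures are tried in a fixed order: heterogeneous Toeplitz, Toeplitz, then AR(1) with a participant random effect. No minimum level size and no merging rule is given. SAP 2.4 allows subgroups to be added before the database is finalized but does not mention combining levels.

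**The concern.** A programmer who codes age from SAP 2.4 gives a 65-year-old a missing age group. That participant drops out of all four within-level models and out of the age interaction model. The age rows of the forest plot would then total fewer participants than, say, the gender rows, with no explanation in the SAP. A programmer who reuses the Table 2 grouping would get a different age analysis. Two readings of one plan should not give two results, and a choice between them made after treatment results are visible would be post hoc.

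The second matter is the youngest level. SAP 1.4 now expects 400 to 480 participants instead of 1,900, but the four bands were kept and a separate estimate is promised for each. In a heart failure population the 18-25 level may be very small, and the SAP does not say what happens then.

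**Working it through.** **Coverage of ages.** Assume age is recorded in completed years.

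| Age | SAP 2.4 | SAP Table 2 |
|---|---|---|
| 18 to 25 | level 1 | level 1 |
| 26 to 50 | level 2 | level 2 |
| 51 to 64 | level 3 | level 3 |
| 65 | none | level 4 |
| 66 and over | level 4 | level 4 |

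Age 65 is the only eligible whole-year age without a level in 2.4. With ≥65, every age from 18 up is covered.

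**Number affected.** The documents give no age counts, so the share aged 65 is an assumption. At 1% the number is 0.01 × 400 = 4 to 0.01 × 480 = 4.8. At 4% it is 0.04 × 400 = 16 to 0.04 × 480 = 19.2. The range is about 4 to 19.

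**The plan's own figure.** No figure is stated for any age band. The nearest is the power in SAP 1.4, which fixes the SD of 18 used below. With 950 per arm and a difference of 3, power = Φ(3 / (18 × √(2/950)) − 1.96) = Φ(3.632 − 1.960) = 95.3%, against a stated figure of approximately 95%. It reproduces.

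**Size of the within-level model.** Fixed effects: intercept 1, treatment 1, time 3, treatment-by-time 3, baseline 1, stratum 1, total 10. Unstructured covariance over four visits: 4 × 5 / 2 = 10 parameters. Each participant supplies up to four visits, so counting people against parameters is the wrong test. What matters is whether the 4 × 4 residual matrix has full rank. With arm-by-visit means removed, its rank is n − 2 up to a maximum of 4, so at least 6 complete participants are needed. Allowing for baseline and stratum, about 8 are needed.

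**Chance of fewer than 8 aged 18-25.** With assumed share s, the count is binomial(N, s).

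| Assumed share | Expected, N=400 | P(<8), N=400 | Expected, N=480 | P(<8), N=480 |
|---|---|---|---|---|
| 0.5% | 2.0 | 0.999 | 2.4 | 0.997 |
| 1% | 4.0 | 0.95 | 4.8 | 0.89 |
| 2% | 8.0 | 0.45 | 9.6 | 0.26 |
| 3% | 12.0 | 0.09 | 14.4 | 0.02 |

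**Precision when the model does fit.** With n participants split equally, SD 18 and n − 4 degrees of freedom, the 95% half-width is 18 × √(4/n) × t(0.975, n − 4). For n = 8 this is 18 × 0.707 × 2.776 = 35.3 points. For n = 10 it is 27.9 and for n = 20 it is 17.1. The trial's target difference is 3 points. Baseline adjustment would narrow these somewhat, but not to a useful width.

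**The case against.** The mismatch is probably a one-character slip. Table 2 has the same lower bands and closes the gap, so the intended cut is visible in the same document. A ≥ sign lost when the PDF was read cannot be excluded either, although it survived in Table 2 and in the step-count rule of SAP 5.3.1. This lowers the seriousness. It does not remove the need for a correction, because as it reads 2.4 is the text that defines the analysis.

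The consequence is also narrow. The subgroup analyses check consistency of the overall effect; sample size, primary test and error control are unaffected. That stands in full.

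Three stronger readings are tempting, and the documents do not support them.

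- A reader might infer that 65-year-olds are lost from the subgroup analyses in general. They remain in the primary model and in the region, gender, race, diabetes and ejection-fraction subgroups.
- A reader might infer that the 18-25 level is certainly too small to fit. Without an age distribution this is conditional: at N = 400 the chance of fewer than 8 people falls from 0.95 at a 1% share to 0.09 at 3%. The SAP's covariance fallbacks also ease the parameter count, although they cannot rescue an empty arm or a handful of people.
- A reader might infer that the age interaction test is materially weakened and that the four bands should give way to a single cut at 65. No power loss has been calculated. An empty level adds no degree of freedom, and the interaction model pools its covariance across levels. A single cut would also discard the 26-50 and 51-64 levels, which nothing in the documents shows to be sparse.

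**Conclusion.** The age-band error stands on the text alone. SAP 2.4 excludes age 65 from the age levels, Table 2 includes it, and the two must agree. About 4 to 19 of 400 to 480 participants would be missing from the age rows and the age interaction test if 1% to 4% are aged 65. Those shares are assumptions, as is recording age in whole years.

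The sparse-level point is secondary and conditional. At 400 to 480 participants the 18-25 model probably cannot be fitted if about 1% or fewer are in that band. At 2% to 3%, with 8 to 14 people expected, a fit may be possible but the interval would be roughly 20 to 35 points either side. What the documents do establish is that no rule covers this case.

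Severity is minor: the primary conclusion cannot change.

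**What to change.** In SAP 2.4, change >65 to ≥65 so that the age levels match Table 2. This costs one character and changes no other analysis.

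In SAP 5.2.3, add before unblinding that an age level with fewer than a stated number of participants per arm is merged with the adjacent band (18-25 with 26-50) for both the within-level model and the interaction test. The decision should use counts only, without sight of outcomes by treatment. The SAP authors should choose the number; about 8 complete participants in total is only the floor for estimating the model, not a size that gives a useful interval. The documents give no counts from which to size the merged band, so the rule should apply to the merged level as well. The cost is one sentence and slightly less age detail in the forest plot. The four bands can stay as they are in Table 2.

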2.5. Study Day and Relative Day

Study Day 1 refers to the start of the first study intervention administration. All assessments recorded via the smartphone/mobile app and/or Fitbit device will be assigned a day relative to this date.

Relative day for a specific time-point of measurement is defined as:

- measurement date - (date of Study Day 1) +1, if measurement date is \geq date of Study Day 1
- measurement date - date of Study Day 1, if measurement date < date of Study Day 1.

2.6. Baseline, End of Treatment, and End of Study

Baseline is defined as the last observation made prior to the start of the first study intervention administration. End of Treatment (EOT) observation will refer to the last observation made prior to and including the day of the last dose of study intervention, regardless of when the last dose is taken. For the PRO measurements, EOT observation will include the last observed value prior to the last dose of study intervention, and/or, within a measurement window allowed by the app that may overlap the last dose date (i.e., may extend the last dose date by a few days). For the daily

activity data, it will represent average from the last 14 days prior to the last dose taken, regardless of when the dose is taken.

The EOS value is defined as the observation that is taken on the date of very last available postbaseline data in the study period. Unscheduled measurement results are included in this definition and will be considered as the last timepoint value if the unscheduled measurement result is the last postbaseline result available within the analysis period.

2.7. Imputation Rules for Missing AE Date/Time of Onset/Resolution

Claims data are generally based on service dates and not on start and end dates for adverse events. Consequently, no imputation rule for missing AE dates can be applied.

3. INTERIM ANALYSIS AND DATA MONITORING COMMITTEE REVIEW

No interim analysis is planned in this study. However, data from the 12-week double-blind treatment period will be summarized/analyzed and reported out first as soon as the last randomized participant has completed the treatment period. Data from the full 9-month study period will be reported after the follow-up is completed on all study participants.

4. SUBJECT INFORMATION

The number of participants in each analysis set will be summarized and listed by intervention group, and overall. In addition, the distribution of participants by region within the US and recruiting networks will be presented, unless otherwise noted.

4.1. Demographics and Baseline Characteristics

Table 2 presents a list of the demographic variables that will be summarized by each intervention group, and both combined for the full analysis set (FAS). Demographics will also be summarized by various IHNs (or regions) using the FAS as well as the all randomized analysis set.

Table 2: Demographic Variables

Continuous Variables:	Summary Type	
Age (years)	Descriptive statistics (N, mean, standard deviation [SD], median and range [minimum and maximum], and IQ range). Frequency distribution with the number and percentage of participants in each category.	
Categorical Variables		
Age (18-25 years, 26-50 years, 51-64 years, and ≥65 years)		
Sex (male, female)		
Race ^a (American Indian or Alaska Native, Asian, Black or African American, Native Hawaiian, or, other Pacific Islander, White, Other)		
Diabetes status at baseline (T2DM or no T2DM)		
HF ejection fraction type (HF _r EF or HF _p EF)		

^a If multiple race categories are indicated the Race is recorded as 'Multiple'.

4.2. Disposition Information

Total number of screened participants and number of screen failures will be provided. The total number of participants randomized into the study will be provided. Randomized participants who complete the 12-week, double-blind treatment period and who do not discontinue study intervention prematurely are considered study intervention completers.

The number of participants in the following disposition categories will be provided for the 12-week, double-blind treatment period by intervention group and overall:

- participants randomized
- Participants treated with study agent.
- participants receiving study intervention
- participants completing the double-blind treatment period
- participants who discontinued study intervention
- participants who terminated study prematurely
- reasons for discontinuation of study intervention and termination of study
- participants who were unblinded during the double-blind treatment period.

The distribution of the time to study termination for the 12-week, double-blind treatment period will be displayed with Kaplan-Meier curves. Participants who terminate study participation prematurely at any time will be considered an 'Event' and their date of study termination will be used in the time to study termination calculation. In this analysis, participants who complete the 12-week, double-blind treatment period will be considered 'censored' and the date of double-blind treatment period completion will serve as the time of censoring.

4.3. Treatment Compliance

Participants will be instructed and notified by the study app weekly to confirm the number of study intervention capsules that they took that week. Study intervention compliance data will be monitored bi-weekly for ensuring compliance is >80%.

Compliance with the study intervention is defined in this study in terms of the total number of doses received during the total treatment period of 12 weeks and not in terms of maintained drug concentration while participating in the study. Participants who take study intervention as instructed >80% of the total study intervention duration will thus be considered compliant.

For the double-blind study intervention period, compliance (%) = $100 \times \text{number of days taking study intervention (pills)} / \text{total study intervention duration (including days off study intervention)}$.

The number and percentage of participants who have >80% study intervention compliance through Week 12 (end of double-blind treatment period) will be provided by randomized group.

4.4. Extent of Exposure

The number and percentage of participants who receive study intervention will be summarized by randomized group.

Descriptive statistics for study intervention duration (N, mean, SD, median, and range [minimum, maximum]) will be presented by randomized group based on the safety analysis set. Person-years of exposure to study intervention are calculated [as days of intervention/365.25] and will be presented by randomized group.

Duration of study intervention will be summarized in the following duration categories: [<1 week, 1-<2 weeks, 2-<3 weeks, ..., 11-≤12 weeks] by randomized group and presented graphically in a histogram.

Cumulative study intervention exposure [≥1 week, ≥2 weeks, ..., ≥12 weeks] will also be summarized.

Study intervention duration is defined as (date of last dose of study intervention – date of first dose of study intervention) +1.

4.5. Protocol Deviations

In general, a list of major protocol deviations will be produced for the final clinical study report (CSR) and these major deviations from protocol may have the potential to impact participants' rights, safety, or well-being, or the integrity and/or result of the clinical study. Participants with major protocol deviations will be identified prior to database lock and summarized

4.6. Prior and Concomitant Medications

In this pragmatic virtual study, other than history on prior medications up to 36 months, no additional information including specific start/end dates of using prior medications will be available. However, dates of prescription-fills for specific concomitant/prohibited medications collected through the claims/pharmacy database for the duration of the study may be available. The concomitant medication use during study may be categorized into broad classes of **glucose-lowering agents** (such as insulin, metformin, sulfonylurea, DPP-4 inhibitor, GLP-1 receptor agonist), **renal and cardiovascular (CV) protective agents** (such as RAAS inhibitor [including sac/val], statin, antithrombotics, beta-blockers, diuretics, IV in-patient diuretics, vasodilators, inotropes, anti-infectives) and **UGT inducers** (such as carbamazepine, phenytoin, phenobarbital, tiprnavir, rifampicin, testosterone, propionate, nelfinavir, ritonavir, efavirenz, lamotrigine) respectively.

5. EFFICACY

5.1. Analysis Specifications

Descriptive statistics for continuous variables include count (n), mean, SD, standard error (SE), median, minimum, and maximum. Descriptive statistics for categorical variables include participant counts and percentages.

5.1.1. Level of Significance

A 5% level of significance will be used for all analyses. All statistical tests and 95% confidence intervals presented in the analyses of endpoints will be 2-sided.

5.1.2. Data Handling Rules

This study will obtain mainly 3 types of data for statistical analysis: the smartphone/app-based PRO data, the activity data collected from the Fitbit device and the claims data on adverse events (including clinical outcomes, prescription fills, and related HRU). In addition, participant's self-reported AE data collected via a Call Center will be directly sent over to Janssen Safety separately and is described below as well. All data will be received and processed by PRA (3rd party vendor, see [Appendix 5: CHIEF-HF Study Data Flow Diagram](#)) into analysis files based on specifications provided by the sponsor/study SAP unless specified otherwise.

Smartphone Data - PRO Measures

PRO data (ie, KCCQ, PGIC and PGI-S, participant satisfaction survey) will be collected via the smartphone apps available with participants. Based on the administration of the KCCQ at screening/baseline through an app, an overall summary score will be produced to decide eligibility of individual participant into the study. The individual domains and summary scores of KCCQ will be calculated using the scoring algorithm provided in the KCCQ manual at specified time points during the study. Missingness in these PRO measures may result from participants not completing the questionnaires on the smartphone app at the scheduled times during the study period for various reasons including non-compliance with the protocol, discontinuation due to AE, loss to follow up, etc.

Missing and incomplete data in KCCQ PRO measure may be of 2 types: missing at the form-level and at the item-level. Form-level missing data refers to a participant missing an entire PRO assessment for a scheduled time point. If not otherwise specified, analyses will be conducted on all available data and form-level missing data will not be imputed. For the KCCQ, derivation of individual domain scores in the presence of missing item-level responses will follow algorithms specified in the KCCQ manual. PRA will calculate baseline KCCQ overall summary score based on the KCCQ app and include in the analysis database. For calculation of all other KCCQ domain scores (including the KCCQ-TSS) at baseline and at all post-randomization time points, scoring instructions available per the KCCQ manual with Janssen will be followed (see Appendix 8). For the PGIC and PGI-S measures, a single imputation (ie, last observed scores carried forward) for missing post-baseline scores will be used as a conservative rule. Vertical file formats will be prepared for all PRO data, reading one record per patient for each measurement time (ie, baseline, Weeks 2, 4, 6, and 12, and Months 6 and 9, respectively).

Fitbit Data - Clinical (Activity) Measures

Data from the Fitbit device pertaining to the daily total step counts and daily total floors climbed will be aggregated over 2-week intervals for the entire study duration (see [Table 1](#)). Due to the general sedentary nature of HF patients, Fitbit recorded <100 steps taken in a day will not be

considered in the calculation of averages for daily step counts . If missing >7 days (50%) in a 2-week interval, the corresponding 2-week interval average will be set to missing.

In case of premature discontinuation of the study intervention, the average of the last non-missing 14-day window prior to the last dose of study intervention will always be used as an EOT value. If the EOT value corresponding to the period (EOT-14, EOT-1) is missing (not valid), the EOT period will be rolled back by one day, ie, (EOT-15, EOT-2), (EOT-16, EOT-3), until a non-missing (valid) value is available. This corresponds to a last observation carried forward (LOCF) up to Week 12/EOT approach. If no post-baseline daily activity data have been collected for at least 7 days over a 14-day time window, no EOT value will be computed, and the post-baseline value will be set to missing.

Baseline for daily step count and daily floors climbed variables will be defined by averaging the daily values over a 14-day interval starting with the first dose date. These data will be organized into a vertical file format to read one record per participant for averages over each 2-week interval during the entire study (including the EOT/EOS values, as applicable).

Claims Data – AEs, HRUs, Clinical Outcomes

Claims data pertaining to AEs of interest (as defined in the protocol), number of prescription fills, HRUs, and clinical outcomes reported with appropriate ICD codes applied at the individual participant level will be organized with one record for each incident (ie, hospitalization, etc.) date. Adverse events of interest include all severe hypoglycemic events, acute kidney injury, fractures, diabetic ketoacidosis, and lower limb amputation.

In addition, the following adverse events will be examined: hypotension; Fournier’s gangrene; genital mycotic infections; urinary tract infections (including urosepsis and pyelonephritis); increased urination; and hypersensitivity reactions including angioedema and anaphylaxis.

Self-reported AE data – Data from participants self-reporting adverse events (AEs) to a Call Center (set up by Care Innovations) will be manually submitted directly to the Sponsor (i.e. Janssen Safety [GMS]) for appropriate evaluation and analysis. Janssen Safety (GMS) will extract participant-reported AEs and transfer data to PRA for upload into the CCDS. Self-reported events will be captured from the date of the first dose of study intervention through the end of treatment (Month 3) plus 30 days. A listing of these self-reported AE may be produced based on available data.

